In recent years lavender has been studied on human subjects to tests its known reputation for sedative, anxiolytic, and analgesic properties. In one clinical trial oral administration of lavender was compared to Ativan 0.5mg for generalized anxiety disorder. The study supported that the oral lavender oil called Silexan was as effective as 0.5mg of Ativan in adults with generalized anxiety disorder [5]. A second clinical trial analyzing sleep quality found that ischemic heart patients in the intensive care unit received better sleep with 100% lavender oil undiluted placed on a cotton ball within 20cm from the patient from the hours of 9pm-6am [6]. Two studies have used lavender oil through inhalation in the recovery room with an oxygen mask after surgery for pain control. The first study was patients after breast biopsy, the second was patients who just had laparoscopic adjustable gastric banding [7,8]. The study with the breast biopsy patients showed a higher satisfaction rate with pain. The patients undergoing laparoscopic banding also showed a higher rate of satisfaction with pain as well as decreased opioid use in the recovery room. Furthermore one study used 100% lavender oil undiluted on the skin of pediatric patients undergoing tonsillectomy as a topical application and asked the patients to inhale. The study showed a decrease use in Tylenol usage postoperatively [9].

4. Design & Procedures:

Design

Randomized study with control group and test group. Using a 1:1 treatment allocation ratio, the total of 60 patients (30 per arm) will be randomly assigned to control or treatment arm. The Statistical Investigator will generate the randomization scheme and monitor the randomization process over the course of the trial. The study will use randomization with random permuted blocks. The test group will receive 50% lavender oil diluted in fractionated coconut oil and the control group will have the current standard of care with no essential oil intervention (coconut oil only) will be applied. Fractionated coconut oil is being used because it is colorless, odorless, does not stain clothing, and has a long shelf life. It also serves as a carrier oil for the essential oil to absorb into the skin instead of evaporating off the skin due to essential oils volatile nature.

Study Procedure

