During surgery the patient will receive 4 drops of 50% solution lavender oil on the temple region over the temporal artery every 2 hours until completion of surgery. This will be applied by the anesthesia team. If the temporal region is not accessible the shoulders or feet will be alternate locations of application. When the patient arrives to the recovery room she will receive lavender oil through an oxygen mask. A 50 % solution will be used by placing 4 drops of the lavender solution on the mask and wiping it around the mask with a cotton ball. This delivery method will be used because this was used in a study from New York University Medical Center studying postoperative pain and no adverse events occurred [7]. When the patient is on the post-operative floor she will receive 50 % lavender oil on the wrist every 4 hours in the same manner as preoperatively from the hours of 6am to 9pm. Nightly (9pm-6am), 8 drops of 50% lavender oil will be placed on the cotton ball situated within 20cm of the patient. This method and concentration was chosen after reviewing a study in ischemic heart patients in the intensive care unit. The patients received lavender at bedside on a cotton ball and had statistically significant better sleep quality [6]. The control group will have coconut oil applied without any lavender oil applied in the same sequence as listed above. This will ensure the same procedures are carried out under both arms.

Blood pressure, pulse, respiratory rate, and oxygen saturation will be monitored in the preoperative area before lavender is given and 30 minutes after it is given. The level of pain will also be asked prior to application and at the second set of vitals. The control group will get two sets of vital measurements and pain scale measurements without any intervention. The same vitals will be recorded while the patient is under anesthesia every 30 minutes. There will be a notation in the chart when lavender is given to correlate time from application to time of vitals recorded. A review of the electronic medical record will be done to record amount of narcotic needed interop in both groups.

In the recovery room after the patient is given lavender through the oxygen mask the same vital signs and pain score measurement will be taken 15, 30, and 60 minutes from lavender application. In the control group on arrival to the recovery room the same data points will be

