- For coughing or any feeling of shortness of breath or chest discomfort, lavender oil therapy will be stopped. Any lavender applied to the skin will be diluted with fractionated coconut oil as mentioned above.
- For any serious, unexpected event, which occurs to any subject during this study the appropriate DUHS IRB Adverse Event notification will be completed, e-signed by the PI and submitted to the DUHS IRB within 5 days of notification of the reported event.
- Any patient who does not want to participate in the study can decline at any time.
- The patient's demographics including name will remain confidential.

11. Costs to the Subject:

Study intervention and Lavender Oil will be provided to subjects at no additional cost. Subjects and/or their regular insurance provider will be responsible for all procedures and tests considered standard of care for their condition.

12. Data Analysis & Statistical Considerations:

Study Design/Endpoints: The primary outcome will be a difference in pain scores between the 2 groups and/or decrease in narcotic use and/or increased patient satisfaction of pain control. Secondary outcomes are better sleep and decreased anxiety.

Analytic Plan and Method: Differences in the change scores of pain in the two groups as well any other demographic and clinical continuous variables will be examined using t-test or Wilcoxon test, depending on whether the variables are normally or non-normally distributed respectively. The differences between the categorical variables will be examined using chisquared or Fisher's exact test. Analysis will be conducted under the intention to treat (ITT). Missing data will be imputed under multiple imputation methods. Differences in the outcomes while controlling for potential covariates (age, etc) will be examined using linear regression. Significance of the tests will be assessed at alpha = 0.05. Analysis will be conducted using SAS 9.4 (SAS Institute, Inc., Cary, NC.).

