Power and Sample Size Calculations: A study called the effectiveness of lavender essence on sternotomy related pain intensity after coronary artery bypass grafting evaluated the effectiveness of lavender. The study observed pain scores of 6.45 (SD: 2.23) and 4.11 (2.13) in the control and treatment groups respectively [14]. For 80% power at alpha = 0.05, with the above observed means and standard deviations in the control and treatment groups, 15 subjects per group will be needed. Assuming about a 20% drop-out rate, the study would need 17 subjects per group.

13. Data & Safety Monitoring:

Data and safety monitoring will be reviewed by a team of experts (a least 2 physicians will be identified by the PI in this area of research and who are not associated with this study). Adverse events (AE) and serious adverse events (SAE) will be examined by the committee. We plan to have a review of the safety data in a meeting when half the study subjects are recruited into the study. The committee will decide on the continuity of the trial after reviewing the SAEs while ensuring the safety of the patients.

14. Privacy, Data Storage & Confidentiality – see Section 12 of the e-IRB submission form and complete the questions in that section.

References.

- 1. Jane Buckle. Clinical Aromatherapy Essential Oils in Healthcare. Churchill Livingstone Elsevier;2015.2-13.
- 2. N. Vakili and A. Gorji. Psychiatry and psychology in medieval Persia. *Journal of Clinical Psychiatry*. 2006;67:1862-1869.
- 3. A. Gorji and M.K.Ghadiri. History of headache in medieval Persian medicine. *Lancet Neurology*. 2002;1:510-515.
- 4. Aroma Tools. Modern essentials: a contemporary guide to the therapeutic use of essential oils. Utah: Aroma Tools; 2014. 11 p.
- 5. H. Woelk and S, Schlafke. A multi-center, double-blind, randomized study of the lavender oil preparation silexan in comparison to lorazepam for generalized anxiety disorder. *Phytomedicine*. 2010;17: 94-99.
- 6. Moeini M, Khadibi M, Bekharadi R, et al. Effects of aromatherapy on the quality of sleep in ischemic heart disease patients hospitalized in intensive care units of heart hospitals

of the Isfahan university of medical sciences. *Iranian Journal of Nursing and Midwifery Research*. 2010;15:234-239

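### The pain change score has no defined time points, baseline pain is not a named covariate and no pain analysis is ranked primary; a prespecified baseline-adjusted regression would settle all three.

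*Combined protocol and SAP*

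**What the plan says.** Section 12, Study Design/Endpoints, opens: "The primary outcome will be a difference in pain scores between the 2 groups". It then joins narcotic use and satisfaction to pain by and/or, without an order.

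Section 12, Analytic Plan and Method, makes the pain variable a change: "Differences in the change scores of pain in the two groups". This and the other continuous variables "will be examined using t-test or Wilcoxon test, depending on whether the variables are normally or non-normally distributed respectively". It adds an adjusted analysis: "Differences in the outcomes while controlling for potential covariates (age, etc) will be examined using linear regression". Neither analysis is called primary.

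Section 9, Study Interventions, sets the pain schedule. Before surgery: "The level of pain will also be asked prior to application and at the second set of vitals". Controls are measured too: "The control group will get two sets of vital measurements and pain scale measurements without any intervention". In the recovery room, pain is scored at 15, 30 and 60 minutes in both arms. On the floor, the section schedules vital signs every four hours and does not expressly mention a pain score.

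Section 12, Power and Sample Size Calculations, uses group scores from a cited study: "The study observed pain scores of 6.45 (SD: 2.23) and 4.11 (2.13) in the control and treatment groups respectively". Section 4 sets the enrolled size: "the total of 60 patients (30 per arm) will be randomly assigned to control or treatment arm".

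**The concern.** A change score needs a start and an end, and the documents give neither. The choice of start also affects what is estimated. The second preoperative score is taken after the oil has been applied, so a change from it may subtract part of any treatment effect.

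The covariate list is open, and the t-test/Wilcoxon and regression analyses stand side by side unranked. Time points and covariates could therefore be settled after the data are seen, in which case the 5% error rate for pain is no longer fixed.

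The second and smaller stake is precision. Subtracting a baseline score that correlates weakly with the follow-up score adds noise; adjusting for it in a regression does not. The plan was sized on a single score per patient, so its power figure does not carry over automatically to a change score.

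**Working it through.** **Inputs from the documents.** Means 6.45 and 4.11, SDs 2.23 and 2.13, 80% power, alpha 0.05, 20% drop-out (section 12); 30 per arm (section 4); two preoperative and three recovery scores (section 9). **Assumed, because the documents do not give them:** the pre-post correlation ρ, the ratio k of baseline SD to follow-up SD, and the correlations among repeated scores.

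**1. The plan's own figure.** Difference = 6.45 − 4.11 = 2.34. Pooled SD = √((2.23² + 2.13²)/2) = 2.181. A two-sided two-sample t-test needs 14.66, so 15 per group, with power 81.0%. The stated 15 reproduces as a comparison of one score per patient.

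**2. How many changes fit the wording.** Two starting scores × three recovery scores = 6. The preoperative before/after change is a seventh possible reading.

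**3. Precision.** Relative to the follow-up variance:
- change score: 1 + k² − 2ρk
- baseline-adjusted score: 1 − ρ²
- difference between the two: (k − ρ)², which is never negative and is zero when k = ρ

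Example with k = 1, ρ = 0 and 30 per arm. The change-score SD is 2.181 × √2 = 3.084. The noncentrality is 2.34/(3.084 × √(2/30)) = 2.94 on 58 df, giving 82.4% power. For the adjusted score it is 2.34/(2.181 × √(2/30)) = 4.16 on 57 df, giving 98.3%.

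Evaluable at 20% drop-out: 30 × 0.8 = 24 per arm. Power, change vs adjusted:

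| k | ρ | 30 per arm | 24 per arm |
|---|---|---|---|
| 1 | 0 | 82.4% vs 98.3% | 73.0% vs 95.3% |
| 1 | 0.3 | 93.2% vs 99.0% | 86.8% vs 96.8% |
| 1 | 0.5 | 98.3% vs 99.7% | 95.3% vs 98.7% |
| 0.5 | 0 | 95.5% vs 98.3% | 90.2% vs 95.3% |
| 0.5 | 0.3 | 98.7% vs 99.0% | 96.2% vs 96.8% |
| 0.25 | 0 | 97.7% vs 98.3% | 94.2% vs 95.3% |
| 0.25 | 0.3 | 99.0% vs 99.0% | 96.8% vs 96.8% |

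The smallest difference detectable with 80% power at 30 per arm is 2.27 vs 1.60 points at k = 1, ρ = 0, but 1.56 vs 1.53 at k = 0.5, ρ = 0.3.

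**4. Selection.** Trials with no true effect were simulated at 30 per arm, 20,000 per setting, with five multivariate normal scores. Settings: k of 1 or 0.5; pre-post correlation 0, 0.3 or 0.5; correlation among recovery scores 0.5, 0.7 or 0.9; correlation between the two preoperative scores 0.6, 0.8 or 0.95. Share of trials with the smallest p below 0.05:
- one change fixed in advance: about 5%
- three changes from the first preoperative score: 7% to 14%
- six changes from either preoperative score: about 9% to 22%
- those six plus the preoperative before/after change: about 13% to 24%

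With k = 0.25, the top of the six-change range falls to about 16%.

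**The case against.** The strongest reply is that baseline adjustment is an efficiency choice. A t-test on one change score with two fixed time points would also hold the 5% rate, and at 30 per arm every setting above keeps at least 82% power, over the plan's 80% target. Of the settings shown, only k = 1, ρ = 0 with 24 evaluable falls below it. The open covariate list does not exclude baseline pain either. All of this stands, and it is why precision is the smaller harm. It does not supply the missing time points or rank the analyses, and spare patients do not protect against choosing among analyses.

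Four stronger readings are tempting, and the documents do not support them:
- *The change-score test is invalid or biased.* With a pre-application baseline it is valid under randomization.
- *The trial is underpowered for pain.* That needs a correlation and a baseline spread that the documents do not give.
- *The plan commits to both raw and change analyses, so the error inflation is larger still.* The endpoint sentence does not say raw, and the sentence on change scores can be read as defining it. Nor does the plan expressly state a regression on baseline pain. Only changes are therefore counted here.
- *The 9% to 22% range is a ceiling, or a forecast.* It is neither. It shows deliberate selection over six changes; other readings add to it, and a smaller baseline SD lowers its top.

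**Conclusion.** The point holds as an avoidable gap in prespecification, and the plan should be changed. It does not invalidate the trial. The text leaves open which scores form the change, whether baseline pain enters the regression, and which pain analysis leads.

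Until one analysis is fixed, a pain result cannot be read as a single 5% test. The precision gain from adjustment ranges from substantial (about 16 percentage points of power at 30 per arm and 22 at 24, with equal SDs and zero correlation) to immaterial (baseline SD half the follow-up SD or less, correlation about 0.3). The adjusted analysis is essentially never worse, since its only price is one degree of freedom. These sizes rest on the cited study's 2.34-point difference and SD of 2.18 applying here, on normal scores, and on assumed correlations and baseline spread.

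The conclusion concerns pain only. The three primary outcomes joined by and/or are a separate issue, which this change leaves open.

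**What to change.** 1. Settle first whether pain is recorded on the floor, because that decides which postoperative scores are available.
2. Make the linear regression already in section 12 the primary pain analysis. The outcome is one postoperative pain score or summary, chosen by the sponsor and stated in advance (for example one of the three recovery scores, or their mean).
3. Include terms for arm and for the preoperative pain score taken before the first application, not the later preoperative score. Name any further covariate, such as age, in advance.
4. Keep the t-test/Wilcoxon comparison of changes as a sensitivity analysis, with its two time points defined.
5. State that the power calculation is for a single score per patient.

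The cost is one degree of freedom, one decision on the outcome and some wording. The preoperative and recovery scores are already scheduled in both arms, so no extra patients are needed, and no extra assessments if a recovery score is chosen.

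### Each continuous outcome has two unranked analyses, and multiple imputation has no combining rule, so the 0.05 level is not protected

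*Combined protocol and SAP*

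**What the plan says.** All of the analysis text is in Section 12 of the combined protocol and SAP.

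- **Primary outcome.** "The primary outcome will be a difference in pain scores between the 2 groups and/or decrease in narcotic use and/or increased patient satisfaction of pain" (the last component being how satisfied patients are with their pain relief). All three components are numeric. Section 9 takes narcotic amounts from the electronic medical record and has satisfaction rated from 1 to 10.
- **First analysis.** Change scores of pain, and other continuous variables, are compared by "t-test or Wilcoxon test, depending on whether the variables are normally or non-normally distributed respectively". No criterion for normality is given.
- **Second analysis.** "Differences in the outcomes while controlling for potential covariates (age, etc) will be examined using linear regression". The covariate list is open, and age is the only covariate named.
- **Missing data.** "Missing data will be imputed under multiple imputation methods". The population is intention to treat. No imputation model, number of imputations or combining rule is stated.
- **Level.** "Significance of the tests will be assessed at alpha = 0.05".

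Section 9 records pain in the preoperative area before the first application, so a pre-treatment pain value exists. Satisfaction starts on postoperative day 1, and narcotic use is counted from surgery onwards. Neither has a preoperative value.

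**The concern.** Two gaps meet in one paragraph.

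First, each continuous outcome has an unadjusted test and an adjusted regression, and nothing ranks them. If they disagree, the plan does not say which one answers the question, and a reader of the results could not tell whether the choice was made in advance.

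Second, multiple imputation produces several completed data sets, and their results have to be combined. Rubin's rules combine an estimate and its standard error. The t-test and the regression supply both; a Wilcoxon test by default supplies a p-value. If an outcome is judged non-normal, which is plausible for narcotic totals and a 1-10 rating, the analyst must choose a pooling method that the plan does not name. The normality judgement may also differ between imputed data sets. What is at stake is whether a result reported as significant at 0.05 was tested at 0.05.

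**Working it through.** **1. The plan's own figure.** Inputs from Power and Sample Size Calculations: 6.45 (SD 2.23) and 4.11 (SD 2.13), 80% power, alpha 0.05. The difference is 6.45 − 4.11 = 2.34. The pooled SD is √((2.23² + 2.13²)/2) = 2.18, so the standardised effect is 2.34/2.18 = 1.07. A two-sided two-sample t-test needs 14.66 per group, rounded up to 15. The stated 15 is reproduced, and it assumes one test at two-sided 0.05. Section 4 plans 30 per arm, which is used below.

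**2. The normality switch alone.** Simulated at 30 per arm with no true difference, 8,000 runs, Shapiro-Wilk at 0.05 in each arm (an assumption). Monte Carlo standard error: √(0.05 × 0.95/8000) = 0.24 percentage points.

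- Rule-chosen test: 5.0% (normal), 5.0% (rounded 0-10 scores), 4.7% (log-normal).
- Smaller of the two p-values, chosen freely: 5.8%, 5.6%, 6.5%.

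A fixed switch is harmless to the level.

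**3. Two unranked analyses.** Let ρ be the correlation between preoperative and postoperative pain, with equal variances. The change-score estimate has variance proportional to 2(1 − ρ), the baseline-adjusted estimate to 1 − ρ², and their covariance is proportional to 1 − ρ². The two test statistics therefore correlate at √((1 + ρ)/2). The probability that at least one exceeds 1.96 in absolute value follows from the bivariate normal distribution:

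- ρ = 0.2: correlation √0.6 = 0.775, either significant 8.0%.
- ρ = 0.5: correlation √0.75 = 0.866, either significant 7.3%.

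Simulations with the rule-chosen test, normal and log-normal data, 30 per arm and nothing missing gave 6.2-8.6%. Adjusting only for an age-like covariate gave 5.2-6.5%. The documents give no ρ, so 0.2 and 0.5 are assumed values.

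**4. Pooling over imputations.** Rubin's total variance is T = Ū + (1 + 1/M)B, where Ū is the mean within-imputation variance and B the between-imputation variance. Assumptions: 30 per arm, M = 20, 20% of outcomes missing, baseline correlation about 0.3 to 0.4 in most runs, no true difference. At 1,500 runs the Monte Carlo standard error is √(0.05 × 0.95/1500) = 0.56 points. Ranges are over separate simulations.

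| Pooling method | Type I error |
|---|---|
| Wilcoxon z statistic, Rubin's rules | 4.3-4.7% |
| Mann-Whitney probability, Rubin's rules | 5.6% |
| Wilcoxon, mean p-value | 4.4-5.1% |
| Wilcoxon, median p-value | 6.6-8.1% |
| t-test, Rubin's rules | 5.7% |
| Baseline-adjusted regression, Rubin's rules | 3.9-5.9% |

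So the Wilcoxon can be pooled at about the right level, but not by every method an analyst might choose.

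**5. What one adjusted analysis gains.** Take a 0.75 SD effect (assumed; 30 per arm detects 0.74 SD with 80% power when data are complete). With 20% missing, 30 × 0.8 = 24 per arm are observed.

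- ρ = 0.2: change score 0.75/√1.6 = 0.593, power 52%; adjusted 0.75/√0.96 = 0.765, power 74%. Simulated with imputation: 54% and 73%.
- ρ = 0.5: change score 0.75/√1.0 = 0.75, power 72%; adjusted 0.75/√0.75 = 0.866, power 84%. Simulated with imputation: 73% and 83%.

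**The case against.** The strongest reply is that this is ordinary brevity. The text gives one unadjusted test, chosen by distribution, and one adjusted analysis; nowhere does it allow success to be claimed on whichever is significant. Missingness may also be well below 20%: narcotic use comes from the medical record, recovery-room pain is taken within 60 minutes, and stays are typically 1-3 days. At the plan's own effect of 2.34 points with 20% missing, a plain comparison of scores has about 95% power by pooled Wilcoxon z and 96% by pooled t-test.

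Much of this stands. The 6-9% depends on success being read from either result, which the plan neither permits nor rules out, and the pooling figures shrink as missingness falls. The power reply holds only if the true effect is as large as that in the cited cardiac surgery study.

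Some stronger readings are tempting but unsupported:

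- *The Wilcoxon cannot be pooled, so the plan cannot be run.* The z statistic and the Mann-Whitney probability both pool acceptably, and the t-test and regression pool directly.
- *Fisher's exact test is a branch of the primary analysis.* Section 12 reserves it for categorical variables, and all three primary components are numeric.
- *Very large inflation from analysing one imputed data set or stacking them all.* Either would depart from the multiple imputation that the plan requires.
- *Three p-values per outcome.* The text offers t-test or Wilcoxon, not both.

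**Conclusion.** The concern holds as under-specification with a measurable cost. The unranked analyses allow roughly 6-9% type I error per outcome at 30 per arm if success is read from either the chosen test or a baseline-adjusted regression; if only an age-like covariate is adjusted for, the figure is 5.2-6.5%. Median-p pooling of the Wilcoxon gives roughly 7-8%, on the assumption that the 20% drop-out rate in the sample-size paragraph carries over to missing outcomes. The normality switch by itself is not the problem. A reader might infer that the planned analysis is invalid or impossible; the documents do not support that. The stated change-score comparison is also the weaker choice for pain when ρ is 0.2 or 0.5, since the trial already collects the value needed for adjustment. The change should be made before outcome data are examined.

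**What to change.** Amend the Analytic Plan and Method paragraph of Section 12:

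1. **Pain.** Replace the change-score t-test/Wilcoxon switch with one primary analysis: linear regression of the postoperative value on arm and the preoperative value. Use the preoperative score recorded before the first application, because the second preoperative score follows treatment.
2. **Narcotic use and satisfaction.** Use the same regression without the baseline term. For skewed narcotic totals, specify robust standard errors or another scale in advance.
3. **Imputation.** State the imputation model and the number of imputations, fit the regression in each imputed data set, and pool by Rubin's rules.
4. **Covariates.** Replace the open list with a closed one.
5. **Other tests.** Keep the t-test and Wilcoxon as sensitivity analyses that do not decide the conclusion.

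The regression still needs a named postoperative time point or summary, and the and/or primary outcome needs its own rule; both are separate points. The cost is a few lines of text. Regression is already in the plan, SAS 9.4 has standard procedures for it, and no new data or patients are needed.
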